6.9. Statistical Methods Planned

6.9.1. Sample size

Based on the results of a pilot study at Stanford University in which the standard deviation of the percentage $ADC < 0.650 \text{ mm}^2/\text{s}$ in comparable post-CA patients was 8.9%, we estimated that 56 patients would be necessary in each study group to show a 40% reduction in the extent of cerebral ischemia with a power of 80% at a two-sided alpha level of 0.05.

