1. SYNOPSIS

Classification: Academic, Investigator Initiated Trial

Protocol Version and Date: Version 4, 20 Jan 2017

Title of Study: Neuroprotective goal directed hemodynamic optimization in post-cardiac arrest patients: a randomized controlled trial (the NEUROPROTECT post-CA trial)

Participating country: Belgium

Study Centers: 2 (UZ Leuven and ZOL Genk)

Study Period: 3 years

Anticipated start: July 2015

Anticipated completion: May 2018

Objectives:

The **primary objective** of the trial is to assess whether or not a new goal directed hemodynamic optimization strategy can reduce cerebral ischemia in post-cardiac arrest (CA) patients as quantified by diffusion weighted MRI (DW-MRI) to be performed at day 4-5 with quantification of the percentage of ischemic voxels with an apparent diffusion coefficient (ADC) below 0.650 mm²/s.

Secondary efficacy outcomes:

- Cerebral performance category 3-5 at discharge from the ICU CPC 1: return to normal cerebral function and normal living
CPC 2: Disability but sufficient function for independent activities of daily life
CPC 3: severe disability CPC 4: Coma
CPC 5: Death
- Cerebral performance category 3-5 at 180 days post-CA (assessed by trial investigators that are unaware of the treatment assignment)
- SF36 questionnaire at 180 days post-CA (assessed by trial investigators that are unaware of the treatment assignment)
- Neurocognitive testing at discharge from the hospital
- Biomarkers: Neuron specific enolase (day 1-2-3-4-5)

- Functional testing: Activities Daily Life (ADL) and 6 minute walking distance (6MWD) at discharge from the hospital
- Renal function: creatinine day 1-2-3-4-5 and urinary output day 1-2- 3-4-5.
- Length of stay in the ICU
- Duration of mechanical ventilation
- Placement of tracheostomy

Safety outcomes:

- Incidence of life threatening arrhythmias during intervention period
- Incidence of new onset atrial fibrillation during intervention period
- Incidence of pulmonary congestion requiring diuretics during intervention period

Methodology: Prospective, multi-centre, interventional open label investigator driven randomized controlled trial. Randomisation will be stratified by the presence of an initial shockable rhythm.

Number of subjects planned: A total of 112 pts are planned for this study.

Anticipated duration of trial: 3 years from first patient entered to last patient randomized

Diagnosis and main criteria for inclusion and exclusion:

Inclusion criteria:

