4. INTRODUCTION

4.1. The clinical problem

There is absolutely no doubt that sudden cardiac death is a major problem in Belgium in terms of numbers of patients, medical impact and socio-economic impact. Each day, approximately 30 adults suffer from an unexpected out-of-hospital cardiac arrest in Belgium, a number exceeding the incidence of breast or prostate cancer with an estimated 25 new patients per day in Belgium. In addition, many cardiac arrest patients are young (mean age in our hospital 60±12 years, 56% of patients younger than 65 years) with a large economic potential for society. In the community, the occurrence of sudden death often takes center stage through highly mediatised cases of cardiac arrest in young sportsmen with or without a previously undiscovered cardiac anomaly. Apart from the traumatic experience of these dramatic sudden events, only 40% of patients that reach the hospital with spontaneous circulation survive without major neurological impairment or care dependency. An additional 5-10% of the cohort survives with major neurological impairment including a permanent vegetative state. These sobering outcome data and the large economic burden for society (estimated cost of a nursing home facility for these patients approximately 30-50000 €/year) mandate novel treatment strategies that could improve prognosis after cardiac arrest.

Apart from temperature management to avoid fever, no single in hospital randomized controlled intervention trial has improved outcome of these patients. In this way, there is absolutely no doubt that a positive result of the Neuroprotect post-CA trial would be a clear added value for this vulnerable and highly under-investigated patient group.

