6.9.3. General statistics

All data will be managed by the LCC in conjunction with the Steering Committee. Data will be entered and reviewed on an ongoing basis. Key listings and tables will be defined by the Steering Committee. Tables, listings and raw data (as SAS transport files) will be made available to the members of the Steering Committee upon request.

The statistical analysis of the primary and all secondary efficacy endpoints will be performed in the modified Full Analysis Set (FAS), defined as all randomly assigned patients except those withdrawing informed consent for use of all trial data and in case many protocol violations are observed throughout the study, a Per Protocol Set (PPS) will be defined and all efficacy analyses will be repeated on the PPS.

All continuous data will be presented by treatment group using the number of non-missing observations, mean, standard deviation, median and (Q1,Q3). Categorical data will be presented by treatment group using the observed frequencies and percentages for each category.

The primary endpoint (% voxels with ADC < 0.650 mm²/s) will be analyzed by means of an analysis of variance (ANOVA) that includes randomized group and initial shockable rhythm as factors. The treatment effect will be estimated by the difference between treatment groups and presented along with its corresponding 95% confidence interval. Missing values for patients who die prior to the DW-MRI will be imputed on the basis of age, gender, presence of basic life support, presence of initial shockable rhythm, duration of advanced life support, neuron specific enolase, presence of a malign EEG pattern on day 1, final outcome at ICU discharge and allocated treatment arm.

Continuous and normally distributed secondary endpoints will be analyzed by means of an ANOVA including randomized treatment and initial shockable rhythm as factors in the model. Estimated treatment differences will be presented with their 95% confidence interval. Continuous secondary endpoints that show serious deviations from a normal distribution will be analyzed by means of a Van Elteren that includes the initial shockable rhythm as stratification factor. Binary secondary endpoints will be analyzed by means of a stratified Chi-squared test. Treatment differences will be expressed as risk ratios and presented along with their corresponding 95% confidence intervals.

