## 5 Sample Size Determination

Based on the results of a pilot study at Stanford University in which the standard deviation of the percentage  $ADC < 0.650 \text{ mm}^2/\text{s}$  in comparable post-CA patients was 8.9%, it was estimated that 56 patients would be necessary in each study group to show a 40% reduction in the extent of cerebral ischemia with a power of 80% at a two-sided alpha level of 0.05.

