#### **7.4 Methods for Withdrawals, Missing Data and Outliers**

For the primary endpoint, multiple imputation methodology will be used to account for missing data. A total of 100 imputations will be done. The imputation model will include the following:

Age, gender, presence of bystander CPR, presence of initial shockable rhythm, neuron specific enolase at days 1-2-3-4-5, presence of a malign EEG pattern on Day 1 and allocated treatment and death within 7 days of randomisation.

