## 10 Primary and Secondary Endpoints

### 10.1 Primary Endpoint

The primary endpoint will be summarised by randomised treatment group.

Since it is expected that a substantial proportion will have missing data for the primary endpoint (due to early mortality or other reasons), a statistical analysis that does not take account of this missingness is very likely to be subject to considerable bias.

Therefore, missing primary endpoint data will be imputed using the imputation model described in section 7.4.

In each imputation sample, the data will be analysed using an ANOVA that includes a factor for randomised treatment and the stratification factor of shockable rhythm. The results of the analyses will then be combined with standard methodology, using SAS PROC MIANALYZE.

The effect of randomised group will be estimated by the difference between groups and presented along with its associated 95% confidence interval.

The statistical analysis of the primary endpoint will be performed for the FAS and PPS.

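### Does the stated 80% power fail because 56 patients per group includes no visible allowance for missing MRI?

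*Protocol*

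**What the plan says.** Protocol 6.9.1 takes an SD of 8.9% from a pilot study and concludes that "we estimated that 56 patients would be necessary in each study group to show a 40% reduction" with 80% power at two-sided alpha 0.05. SAP 5 repeats the figure: "it was estimated that 56 patients would be necessary in each study group to show a 40% reduction". The Synopsis sets enrolment to match: "A total of 112 pts are planned for this study". None of these places gives a control-group mean, an absolute difference, an expected rate of missing scans or an inflation factor.

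Missing scans are dealt with in the analysis. Protocol 6.9.3 states that "Missing values for patients who die prior to the DW-MRI will be imputed on the basis of age, gender" and further predictors. SAP 7.4 says "For the primary endpoint, multiple imputation methodology will be used to account for missing data", with 100 imputations. SAP 10.1 gives the reason, namely that "it is expected that a substantial proportion will have missing data for the primary endpoint", and analyses each imputed data set "using an ANOVA that includes a factor for randomised treatment and the stratification factor of shockable rhythm". The treatment difference is reported with a 95% confidence interval.

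**The concern.** Planned enrolment equals the calculated number, yet the SAP itself predicts many missing primary values. Usually a calculated number of evaluable patients is inflated for expected loss. If that step was left out, the trial has less than 80% power, and a null or borderline result would be judged against a figure that never applied.

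The background makes the worry natural. Protocol 4.1 reports that "only 40% of patients that reach the hospital with spontaneous circulation survive without major neurological impairment or care dependency", and adds 5 to 10% who survive with major impairment. That leaves 100 − 40 − (5 to 10) = 50 to 55% who do not survive. Imputation does not settle the matter, because it recovers only the information that its predictors carry.

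**Working it through.** **Inputs.** From Protocol 6.9.1 and SAP 5: SD 8.9, n = 56 per group, power 0.80, two-sided alpha 0.05, 40% reduction (read as relative). Not in the documents, so assumed: the share of scans missing m, the variance share R² explained by the imputation predictors, and the variance share r explained by shockable rhythm (part of R², so r cannot exceed R²).

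**1. The plan's own figure.** It cannot be reproduced forwards without a control mean, so I solve backwards.
- Normal approximation: difference = 8.9 × √(2/56) × (1.960 + 0.842) = 4.71; control mean = 4.71 / 0.40 = 11.8%.
- t-test: standardised difference 0.534; difference 0.534 × 8.9 = 4.75; control mean = 4.75 / 0.40 = 11.9%.

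So 56 agrees with the stated inputs if the pilot control mean was near 11.8 to 11.9%. The required n is sensitive to that mean. By the normal approximation it is 78 per group at 10%, 54 at 12% and 40 at 14%.

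**2. If 56 already contains an allowance.** Evaluable patients per group = 56 × (1 − m).

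| Allowance | Evaluable per group | Difference for 80% power | Implied control mean |
|---|---|---|---|
| 10% | 50.4 | 5.02 | 12.5% |
| 20% | 44.8 | 5.33 | 13.3% |
| 30% | 39.2 | 5.70 | 14.3% |

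The control means with and without an allowance lie close together, and nothing in the documents selects among them.

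**3. If 56 is uninflated.** With scans missing completely at random and equal variances, the effective number per group is

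n_eff = 56 / [(R² − r) + (1 − R²)/(1 − m)].

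Example with R² = 0.5, r = 0, m = 0.20: 56 / (0.5 + 0.5/0.8) = 56 / 1.125 = 49.8, and power is 75%. Power for r = 0 and a difference of 4.75:

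| Missing | Observed scans only (R² = 0) | R² = 0.3 | R² = 0.5 | R² = 0.7 |
|---|---|---|---|---|
| 10% | 76% | 77% | 78% | 79% |
| 20% | 71% | 73% | 75% | 77% |
| 30% | 65% | 69% | 72% | 75% |
| 40% | 58% | 63% | 68% | 72% |

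**4. What rhythm adjustment can give back.** If 8.9 is an unadjusted SD, n_eff returns to 56 when r = (1 − R²) × m/(1 − m). At 20% missing this is 0.5 × 0.25 = 12.5% for R² = 0.5, and 0.7 × 0.25 = 17.5% for R² = 0.3. There is a limit. At 40% missing with R² = 0.3, r can be at most 0.30, so n_eff = 56 / (0.7/0.6) = 48.0 and power is at most about 74%.

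**5. The full analysis set.** SAP 6.2 excludes three patients. If 112 were randomised (assumed), 109/2 = 54.5 per group remain, with 79% power when nothing is missing. This loss is negligible.

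**The case for a change.** The strongest argument for acting is that the plain reading of 56 is an uninflated number. On that reading, without a gain from rhythm, every cell of the table is below 80%, even at R² = 0.7. The SAP repeats the 80% unchanged while predicting substantial missingness. The reader cannot tell whether 56 counts randomised or evaluable patients, and a sentence would settle it.

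The reporting gap stands: the stated power cannot be checked from the documents. A demonstrated shortfall does not stand, for four reasons.

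- An allowance inside 56 cannot be excluded (step 2), and rhythm adjustment may offset the loss (step 4).
- The table is illustrative. Its formula assumes scans missing completely at random, whereas the protocol and SAP link missingness to early death. SAP 7.4 puts enolase, EEG pattern and death within 7 days into the imputation model. The formula also ignores the cost of fitting that model in about 112 patients.
- The non-survival figure derived from Protocol 4.1 has no time point and covers all patients reaching hospital with circulation, so it does not estimate loss by day 4-5. Protocol 6.7 keeps patients in full ICU care for at least 5 days with limited exceptions, and Protocol 6.3.2 excludes MRI-incompatible devices.
- Under SAP 4.2 the analysis sets were fixed on 5 March 2018, once all patients had been included. By then the 80% was a planning figure that could no longer alter recruitment.

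**Conclusion.** No change follows. No arithmetic error is shown, since 56 per group fits the stated inputs at a control mean of about 11.9%. What is missing is detail: the control mean, the absolute difference and what 56 counts. In the unfavourable reading (uninflated 56, little variance explained by rhythm, scans missing completely at random, R² 0.3 to 0.7), power would be about 77 to 79% at 10% missing, 73 to 77% at 20% and 69 to 75% at 30%. With an allowance inside 56, or enough variance explained by rhythm, 80% may hold. The documents do not separate these cases.

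None of this alters what the analysts do. The missingness that the SAP expects is addressed by multiple imputation, the stratified ANOVA uses the information in rhythm, and the planned 95% confidence interval will show the precision achieved after all losses. A careful reader will interpret the primary result from that interval and treat the 80% as a design-stage figure. Giving the pilot control mean when the trial is reported would make the calculation checkable, but the validity of the analysis does not depend on it.

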#### 3.4 Blinding of Study Treatment

Health care professionals caring for the patients were aware of the intervention assignment. However, physicians performing neurological prognostication, radiologists interpreting MRIs, study personnel assessing final outcome and the study

statistician were kept unaware of the randomized group up to the moment of the unblinding of the study after database lock.

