### **7.3 Statistical Comparisons between Groups**

Since randomization was stratified by the presence of shockable rhythm, all comparisons between groups should account for this stratification.

So, an ANOVA using factors for randomized group and shockable rhythm will be used rather than a two-sample t-test for the comparison of continuous and normally distributed variables. Continuous variables showing serious deviations from normality will be compared using a Van Elteren test. This test will also be used for the comparison of ordinal data.

For binary and categorical data, a Cochran-Mantel-Haenszel test will be used.

For primary and secondary variables, the effect of treatment will be estimated by an appropriate statistic and presented together with its associated 95% confidence interval.

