#### **7.5 Data Transformations**

Since the main analyses are performed using general estimating equation (GEE) models, no transformation of the data will be necessary since these models are quite robust in the presence of deviations from the normality assumption.

For the analysis of the primary endpoint, data transformation using logtransformation can be considered if the model assumptions of normality and constant variance for the residuals are not met.

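### Do the unstated control mean and the optional log transformation leave the primary analysis and its 80% power undefined?

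*Protocol*

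**What the plan says.** Protocol section 6.9.1 and SAP section 5 carry the same sample size statement: SD 8.9% from a pilot study, 80% power, two-sided alpha 0.05, and "56 patients would be necessary in each study group to show a 40% reduction in the extent of cerebral ischemia". Neither gives the control mean, the absolute difference, or whether the 56 are randomised or scanned patients.

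On the analysis of the primary endpoint:

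- Protocol section 6.9.3 specifies an ANOVA with treatment and initial shockable rhythm, reporting a difference with its 95% confidence interval. It reserves the rank test for other variables: "Continuous secondary endpoints that show serious deviations from a normal distribution will be analyzed by means of a Van Elteren".
- SAP section 10.1 repeats that ANOVA in each imputed dataset: "The effect of randomised group will be estimated by the difference between groups". It also expects a substantial share of missing primary data.
- SAP section 7.3, a general section, says: "Continuous variables showing serious deviations from normality will be compared using a Van Elteren test". It does not exempt the primary endpoint.
- SAP section 7.5 says, for the primary endpoint, that "data transformation using logtransformation can be considered if the model assumptions of normality and constant variance for the residuals are not met".
- SAP section 3.4 says that the study "statistician were kept unaware of the randomized group up to the moment of the unblinding of the study after database lock".

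**The concern.** Read together, these sections seem to offer three analyses for a skewed primary endpoint: a rank test (7.3), an ANOVA on logs (7.5) and an ANOVA on raw percentages (10.1). Each estimates something different: a shift in ranks, a ratio, or percentage points. SAP 7.5 has no threshold, no timing relative to unblinding, no effect measure for the log scale and no scale for the imputation. If the scale were picked with the groups in view, either verdict could be challenged.

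The sample size inputs seem to make this likely rather than remote. The control mean needed to reproduce 56 per group is small relative to the SD, and a percentage cannot fall below zero, so skew is plausible. The stated 80% would then describe only one of the possible analyses, and it says nothing about missing scans.

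**Working it through.** **1. Reproducing the 56.** Inputs from Protocol 6.9.1: SD 8.9, n = 56 per group, power 80%, two-sided alpha 0.05, relative reduction 40%. The control mean is not given, so it is solved for.

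- Difference = (1.960 + 0.842) × 8.9 × √(2/56) = 4.71 points. With the noncentral t it is 4.75.
- Control mean = 4.71 / 0.40 = 11.8%. With the t it is 4.75 / 0.40 = 11.9%.

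The plan's figure is coherent on the raw scale if the control mean is about 11.9% and both groups have SD 8.9. If 56 already includes a 30% allowance for missing scans, the mean is 14.3% by the t calculation.

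**2. Does this imply skew?** At 11.88% a normal model puts Φ(−11.88/8.9) = 9.1% of control patients below zero. With a common SD, the treated mean of 7.13% gives Φ(−7.13/8.9) = 21.2%. If the SD shrinks with the mean, the treated share is also 9.1%. Skew is therefore plausible, but it rests on a back-solved mean and not on a stated one. At that mean, with assumed positive distributions, a Shapiro-Wilk test rejected normality of the raw residuals in 98–100% of simulated trials.

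**3. Is the raw scale the only fit?** No. On the log scale with a proportional reduction, 80% power at 56 per group needs

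- log SD = |ln 0.6| / [(1.960 + 0.842) × √(2/56)] = 0.511 / 0.5295 = 0.965;
- coefficient of variation = √(exp(0.965²) − 1) = 1.24;
- control mean = 8.9 / 1.24 = 7.2%.

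So the inputs do not settle which scale the 80% refers to.

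**4. Power for the planned 40% reduction** (simulation: 56 per group, control mean 11.88%, complete data, two rhythm strata, ANOVA with treatment and rhythm):

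| Assumed shape | Treated SD | Raw | Log |
|---|---|---|---|
| Lognormal | proportional to mean | 94.7% | 97.9% |
| Gamma | proportional to mean | 94.4% | 87.5% |
| Truncated normal | proportional to mean | 93.8% | 68.7% |
| Lognormal | 8.9 | 81.1% | 99.8% |
| Gamma | 8.9 | 79.1% | 99.6% |

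The raw-scale analysis, which is the one specified, has 79–95% in every row. Only the optional log analysis falls clearly below 80%, in one row.

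**5. How often do raw and log give different verdicts at p < 0.05?** With lognormal or gamma data and control mean 11.88%, in about 13–36% of trials at true reductions of 20–30%, and in 4–21% at 40%. For the truncated normal at 40%, the two powers alone force at least 93.8 − 68.7 = 25%.

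**6. Type I error.** With no true effect, each analysis on its own rejects in 4.8–5.2% of trials, so the raw ANOVA is valid despite the skew. Letting the residuals choose between raw and log gave 4.1–5.4%. Deliberately taking the better of the two gives about 7%, and about 8% if the rank test is added. That is an upper bound that assumes selection on the p-value, which the SAP does not allow.

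**7. Missing scans.** If 56 meant complete scans and imputation recovered nothing, raw-scale power would be 76%, 71% and 65% at an assumed 10%, 20% and 30% missing (50.4, 44.8 and 39.2 per group). Against this, a treated SD of 0.6 × 8.9 would give about 92% with complete data, and the imputation uses strong predictors. The direction of the net error is unknown.

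**8. Reading the sections together.** SAP 7.3 is a general rule, whereas 10.1 is written for this endpoint and matches Protocol 6.9.3, which confines the rank test to secondary endpoints. SAP 7.5 itself deals with non-normality of this endpoint by transformation, not by ranks. The live choice is raw or log, and raw is the default.

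**The case for a change.** The strongest case for acting does not need the sample size. SAP 7.5 names the primary endpoint, so it cannot be set aside as a general rule that yields to 10.1. The residual check it describes comes from a model containing treatment, and no masked check is written down. If the data are skewed the option will be triggered, and the choice can turn a positive result into a negative one or the reverse. A few sentences would settle it.

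Part of this stands. The rule is unwritten, and the effect measure and imputation scale for a log analysis are missing. But SAP 7.5 does not say that the check comes after unblinding. Residuals can be examined with coded groups or on pooled values while the statistician is still blinded, and SAP 4.2 records a blinded review meeting before the final analysis, although it is documented only for the analysis populations. A choice based on residuals is also not a choice based on the p-value, and in simulation it did not inflate the error rate. The disagreement figures are largest where power is middling, which is where any two imperfectly correlated tests differ most.

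**Conclusion.** No change to the plan follows. The Protocol and SAP 10.1 give one default primary analysis, a raw-scale ANOVA with a difference in percentage points. It holds its 5% level under the skew considered, and its power for the planned effect is 79–95% at the implied control mean with complete scans. The log option in SAP 7.5 is loosely worded. An analyst would sensibly keep the raw analysis primary and report the log analysis in support, or settle the scale on blinded data with imputation and effect measure to match. Following the plan is not shown to give a wrong result.

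The missing control mean is a reporting gap: it prevents a check of the 80% but does not contradict it. The possible divergence between raw and log (about 13–36% of trials at reductions of 20–30%, 4–21% at 40%) is real but conditional on a back-solved mean of about 11.9%, assumed lognormal or gamma shapes and no missing scans. A truncated normal shape would give more divergence at 40%. A higher control mean would weaken the skew.
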